- bb. Adverse events are collected following signing of the informed consent form at Screening through the last study visit (FU)

CONFIDENTIAL Page 17 of 56

- cc. Perform identification and susceptibility testing at local laboratory for *Candida* for any positive blood culture or positive culture from a specimen obtained from a normally sterile site at Screening and for any positive culture requiring a change of antifungal therapy (ie, identification and susceptibility testing not required for *Candida* isolates cultured from specimens obtained on other study days without a required change in antifungal therapy).
- dd. Blood for culture must be obtained as part of the standard of care for inclusion in the study. Established mycological diagnosis of candidemia and/or IC sufficient for inclusion in the study is defined as ≥1 blood culture positive for yeast or *Candida*, a Sponsor-approved rapid IVD test positive for *Candida* spp, or a positive Gram stain for yeast or positive culture for *Candida* spp. from a specimen obtained from a normally sterile site ≤96 hours before randomization. Record species and susceptibilities for all bacteria isolated within 1 week prior to randomization from blood or any other normally sterile site. If the positive blood culture used to qualify the subject for the study is drawn >12 hours from randomization, then an additional set of blood cultures must be obtained ≤12 hours before randomization.
- ee. Obtain blood and/or normally sterile tissue/fluid for culture if demonstrating mycological eradication or if clinically indicated. Blood cultures should be repeated daily (preferred) or every other day until 2 negative blood cultures are obtained ≥12 hours apart, without an intervening positive culture. All fungal isolates cultured from blood and normally sterile tissue/fluid from Screening through the last study visit must be sent to the Central Laboratory. Record the species and susceptibilities for any new bacteria isolated from blood or any other normally sterile site.

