The overall success rate is the proportion of subjects with success out of the total number of subjects evaluated.

CONFIDENTIAL Page 19 of 56

Mycological Response

Mycological response will be programmatically determined from the electronic case report form (eCRF) and central mycology data at Day 5, Day 14 (± 1 day), Day 28 (± 2 days; only for subjects with IC) and FU (Days 45-52 or Days 52-59 for subjects with IC), according to the definitions in Table 1-3. Determination of the identification of fungal pathogens will follow the process defined in SAP Section 4.

Table 1-3: Mycological Response Definitions

Mycological Response	Definition	
Success (eradication/presumed eradication) *	 If positive blood culture at baseline: The last blood culture drawn on or prior to the day of assessment and another blood culture drawn at least 12 hours prior are both negative for Candida spp and both blood cultures were drawn after initiation of study drug, AND 	
	 Any intervening blood cultures drawn between the 2 qualifying negative blood cultures are also negative for Candida spp. 	
	 If positive culture from a normally sterile site at baseline: Documented mycological eradication: culture on day of assessment from all normally sterile sites of baseline Candida infection (if accessible) is negative OR if no culture on the day of assessment, the most recent culture obtained after the initiation of study drug is negative, OR 	
	o Presumed mycological eradication: follow-up culture is not available (eg, normally sterile baseline site of Candida infection not accessible) or the most recent culture obtained after the initiation of study drug is positive in a subject with a successful clinical outcome (ie, did not receive rescue antifungal treatment and has resolution of systemic signs of invasive candidiasis that were present at baseline) and resolution or improvement of any baseline radiographic abnormalities due to invasive candidiasis,	
	 AND There was no change of antifungal therapy for the treatment of candidemia and/or invasive candidiasis, AND 	
	The subject is not lost to follow up on the day of assessment.	
	Note : Subjects with positive cultures from both blood and a normally sterile site will need to meet success criteria for both blood and normally sterile site to be considered success.	

CONFIDENTIAL Page 20 of 56

Mycological Response	Definition		

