Failure	 If positive blood culture at baseline: The last blood culture drawn on or prior to the day of assessment or any blood culture drawn prior to and within 12 hours of the last blood culture is positive for Candida spp and both blood cultures were drawn after the initiation of study drug OR The most recent blood culture drawn at least 12 hours prior to the last blood culture is positive for Candida spp. and culture was obtained after the initiation of 		
	study drug. OR If positive culture from a normally sterile site at baseline: Documented mycological persistence: culture on day of assessment from all		
	normally sterile sites of baseline Candida infection (if accessible) is positive, OR		
	o Presumed mycological persistence: follow-up culture is not available (eg, normally sterile baseline site of Candida infection not accessible) or the most recent culture obtained after the intiation of study drug is positive in a subject without a successful clinical outcome or with continued (from baseline) radiographic abnormalities due to invasive candidiasis,		
	OR • The subject requires a change of antifungal therapy to treat candidemia, OR		
	The subject dies of any cause prior to or on the day of assessment.		
Indeterminate	• If positive blood culture at baseline: A blood specimen was not available to culture or the result was not available.		
	• If positive culture from a normally sterile site at baseline: A sterile site/fluid post-baseline specimen was not available to culture or the result was not available AND an assessment of signs of invasive candiasis was not available.		
* D 1 1' .'	Subject is lost to follow-up on the day of assessment.		

^{*} Presumed eradication is defined only for a culture from a normally sterile site and is not defined for a blood culture.

Table 1-4 provides examples of timing of the blood cultures and how these are used for determination of the mycological response.

CONFIDENTIAL Page 21 of 56

Table 1-4: Examples of Timing of Blood Cultures

	Blood Cultures	Mycological Response [1]
Example 1	Day of Assessment: Day 14 (T=0 hours) Blood cultures: T=0 (N), T= -18 (N)	Success (eradication)
Example 2	Day of Assessment: Day 14 (T=0 hours) Blood cultures: T=0 (N), T=-10 (P) T=-18 (N)	Failure
Example 3	Day of Assessment: Day 14 (T=0 hours) Blood cultures: T= -20 (N), T= -28 (N) T= -34 (P)	Failure

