Indeterminate	Study data are not available for the evaluation of efficacy for any reason including: • Lost to follow-up, • Withdrawal of consent, • Extenuating circumstances that preclude the classification of clinical outcome of candidemia and/or IC.

AE = adverse event; IC = invasive candidiasis; IV = intravenous.

The cure rate is the proportion of subjects with a cure clinical response out of the total number of subjects evaluated.

Exploratory Mycological Response

Exploratory mycological response will be programmatically determined from the electronic case report form (eCRF) and central mycology data at Day 14 (± 1) and will be defined similarly to mycological response with only 1 blood sample used in the derivation. The responses will be derived according to the definitions in Table 1-6.

CONFIDENTIAL Page 23 of 56

^{*} Prolonged antifungal therapy is defined as therapy for the treatment of candidemia extending beyond the allowable 21 days for study drug or for the treatment of IC extending beyond the allowable 28 days of study drug. The determination of prolonged therapy will only apply to the Follow-up visit clinical response assessment.

Table 1-6: Exploratory Mycological Response Definitions

Exploratory Mycological Response	Definition	

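### The mycological response table does not say how to rate a subject who withdraws consent after early negative cultures, and its Failure row omits a change of therapy for invasive candidiasis

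*SAP*

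**What the plan says.** All of this is in SAP Section 1.2.6.1 unless stated otherwise.

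- **Look-back for blood.** Table 1-3 bases Success on "The last blood culture drawn on or prior to the day of assessment and another blood culture drawn at least 12 hours prior", both negative and both drawn after study drug began. No maximum age is set. The sterile-site rule likewise accepts the latest negative culture when there is none on the day.
- **When cultures stop.** Table 1-1, note ee (Section 1.2.5): "Blood cultures should be repeated daily (preferred) or every other day until 2 negative blood cultures are obtained". A Day 14 response will therefore often rest on cultures from the first week. Note ff requires a blood culture at Follow-up.
- **Subjects who have left.** Success requires "The subject is not lost to follow up on the day of assessment". The Indeterminate row has the matching entry, "Subject is lost to follow-up on the day of assessment". The Success and Indeterminate rows of Table 1-6 repeat both.
- **Other Indeterminate entry for blood.** "A blood specimen was not available to culture or the result was not available". No assessment day is attached to it.
- **Clinical response.** Table 1-5 gives "Withdrawal of consent" as a reason for Indeterminate, on a separate line from loss to follow-up.
- **Change of therapy.** The Success row of Table 1-3 requires: "There was no change of antifungal therapy for the treatment of candidemia and/or invasive candidiasis". The Failure row says: "The subject requires a change of antifungal therapy to treat candidemia".
- **Missing data.** Section 3.10 makes a missing response Indeterminate unless the subject has already failed, and keeps Indeterminate subjects in the denominator.

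**The concern.** Because the response is derived by program, the table's wording is the algorithm. A look-back with no age limit needs a rule for subjects who are no longer observed, since later relapse or rescue would not be recorded. Table 1-3 has that rule for one kind of departure only. Two subjects with identical data would then be rated differently according to the disposition code, and nothing in the SAP explains the difference. The error runs one way: it credits eradication to people whose later course is unknown.

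The second gap has the same origin. The Success and Failure rows describe a change of therapy over different indications, so they do not meet, and some IC subjects fall between them. Mycological success is a secondary objective (Section 1.1.2), and mycological response also feeds overall response through Table 1-2.

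**Working it through.** **The plan's own figure.** Section 3.1 gives 53.8% to 87.5% for 73% success in 30 subjects. The Clopper-Pearson limits are Beta(0.025; x, n−x+1) and Beta(0.975; x+1, n−x). With x = 0.73 × 30 = 21.9 they are 53.8% and 87.5%, so the figure reproduces. It is not in dispute and serves only as the scale below.

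**Applying Table 1-3 literally**

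| Case | Success row | Failure row | Indeterminate row | Result |
|---|---|---|---|---|
| Candidemia, negative cultures Days 3 and 4, consent withdrawn Day 8, assessed at Day 14 | met | not met | not met | Success |
| Same data, contact lost instead | barred | not met | met | Indeterminate |
| Same withdrawn subject, at Follow-up | met | not met | arguably met (required culture absent) | two categories, no precedence |
| IC, latest site culture negative, therapy changed for IC | barred | not met | not met | none |
| IC, no follow-up culture or latest culture positive, rescue therapy given | barred | met (presumed persistence) | not met | Failure |

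**Why the specimen entry does not settle Day 14.** If it meant that no culture was drawn on the day, it would contradict Table 1-4, Example 4. There the cultures are 20 and 68 hours before the assessment and the result is Success. Nor does the schedule require a Day 14 blood culture once two negatives are in hand. At Follow-up note ff does require one, so there the entry has a real claim.

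**Size of the first gap.** Moving w subjects from Success to Indeterminate in an arm of n lowers the rate by w/n, because they stay in the denominator.
- n = 30 (Part A arm): 1/30 = 3.3 points each.
- n = 60 and n = 110 (the combined CD101 sizes in Section 3.1): 1/60 = 1.7 and 1/110 = 0.9 points each.

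Illustration with n = 30 and 22 successes. The 73% is the SAP's overall success rate, borrowed because no mycological rate is given. The values of w are assumed.

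| w | Rate | 95% CI |
|---|---|---|
| 0 | 22/30 = 73.3% | 54.1–87.7 |
| 1 | 21/30 = 70.0% | 50.6–85.3 |
| 2 | 20/30 = 66.7% | 47.2–82.7 |
| 3 | 19/30 = 63.3% | 43.9–80.1 |

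**Size of the second gap.** The change in the success rate is zero, because these subjects already fail the Success row. What is undefined is their mycological category. Table 1-2 has no row for a subject without one, so their overall response is undefined too.

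**The case against.** Several counter-arguments have weight.

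- **Loss to follow-up may be meant broadly.** The phrase is tied to a status on the assessment day. The censoring rules for time to negative blood culture (Sections 1.2.6.1 and 5.3.3.2) also name only loss to follow-up and other antifungals, which suggests a general use. This stands as an ambiguity. It does not remove the problem, because Table 1-5 separates the two reasons and a program working from disposition codes would too.
- **Section 3.10 may catch these subjects.** Not clearly. It acts on missing responses, and here the look-back returns one.
- **An early departure may be rated by design.** Section 1.2.3 calls for End-of-Treatment (EOT) assessments when study drug stops early, and Table 3-2 lets an EOT efficacy assessment stand for Day 14. This stands, and any repair must respect it.
- **The IC omission is a dropped phrase with clear intent.** Probably so: the Success row and the overall-response text both include IC. One could also send such a subject to Indeterminate through Section 3.10. But that would record a change of therapy as missing data, and the programmer would be choosing.

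A reader might also infer more than the documents support:

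- **That the primary outcome is inflated.** Table 1-2 gives Indeterminate when signs were not assessed. The exposure is confined to cases where an EOT assessment stands for Day 14.
- **That withdrawn subjects are plainly Successes at Follow-up.** The required culture makes this a conflict between two rows.
- **That rescued IC subjects in general escape Failure.** Those with no culture or a positive latest culture are already Failures.
- **That they vanish from a table of reasons for mycological failure.** None is planned. The reasons tables in Section 5.3 cover overall and clinical response, and both include Indeterminate subjects.
- **That the 20% discontinuation rate in Section 3.1 bounds the number of withdrawals.** It describes the loss from about 114 randomized to 90 mITT subjects, not attrition within mITT.

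**Conclusion.** Both gaps are present in the text, and both are modest.

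On a literal reading, a cleared subject who withdraws consent is a mycological Success at Day 14 and has two competing ratings at Follow-up, while the same data with contact lost are Indeterminate. The bias favours success. It amounts to 3.3 points per subject in an arm of 30, less in the pooled groups, and zero if nobody withdraws after clearing. The SAP gives no withdrawal rate, so the total cannot be estimated. The outcome is secondary and the study is descriptive.

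The second gap leaves IC subjects with a negative latest site culture and therapy changed for IC without a mycological category. Provided they stay in the denominator, no success rate moves; the Failure count and the overall response category remain undefined.

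No claim is made about the Failure row of Table 1-6, whose text could not be read in the copy examined.

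**What to change.** 1. In the Success and Indeterminate rows of Tables 1-3 and 1-6, replace the loss-to-follow-up condition with: *no longer in the study (lost to follow-up, consent withdrawn or otherwise withdrawn) on the day of assessment*. Make an exception where an EOT efficacy assessment stands for Day 14 under Table 3-2.
2. Reconcile the Failure bullet of Table 1-3 with the Success row, so that a change of therapy is described in both as being for candidemia and/or invasive candidiasis.
3. State the order of precedence: Failure over Indeterminate, and Indeterminate over Success. This also resolves the conflict at Follow-up.

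The cost is a few words of SAP text and one disposition flag in the response program. The downside is a slightly lower mycological success rate if any such subjects exist. The change is best made before the data concerned are unblinded, so that the handling is not chosen with results in view.

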APACHE = Acute Physiology and Chronic Health Evaluation; ECG = electrocardiogram; EOT = End-of-Therapy; ESCMID = European Society Clinical Microbiology and Infectious Disease; FU = follow-up; IC = Invasive Candiasis; IDSA = Infectious Disease Society of America; IV=Intravenous; IVD = in vitro diagnostic; PK = pharmacokinetic.

- a. Study Day 1 is the first day of study drug administration; subsequent study days are consecutive calendar days.
- b. The time windows on Study Day 8, 14, 15, 22, and 28 visits apply only to subjects already stepped down to oral therapy and discharged from the study site.
- c. Perform if further therapy is clinically indicated; only for subjects with IC (with or without candidemia). Subjects will be considered to have IC if there is a positive culture for *Candida* spp. from a normally sterile site other than blood or if there is a positive sponsor-approved rapid IVD or blood culture for *Candida* spp. combined with radiographic evidence of IC.
- d. The Day 28 visit is only for subjects with IC (with or without candidemia). Note that the Day 28 (±2 days) visit could be the same visit as the EOT visit if the subject receives ≥26 days of therapy.
- e. Written informed consent must be obtained prior to initiating any study related assessments or procedures.
- f. Medical history for the last 5 years and *Candida* risk factors for the last 3 months (eg, central line, active malignancy, broad-spectrum antibiotic therapy, diabetes mellitus, immunosuppression, major surgery, total parenteral nutrition, transplant recipient, trauma, dialysis, burns, pancreatitis) and Intensive Care Unit admission and discharge (if applicable). Short-term central venous catheters (eg, peripherally-inserted central catheters, internal jugular or subclavian central venous catheters) and long-term central venous catheters (eg, tunneled catheters) are recommended to be removed within 48 hours after diagnosis with candidemia, consistent with IDSA and ESCMID guidelines
- g. Physical exams are required at Screening, on Day 14, Day 28 (±2 days; only for subjects with IC), and at the FU visit. Height is recorded at Screening. Weight is recorded at Screening, on Day 14, and at the FU visit. If a physical exam is performed at any other visit, abnormal findings that represent a new or worsening condition as compared to baseline should be recorded as an adverse event.
- h. Calculate Child-Pugh score only if the subject has a history of chronic cirrhosis

CONFIDENTIAL

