4. PATHOGEN DETERMINATION

Fungal pathogen determination from blood specimens is based on the genus and species identification of isolates. If the genus identification is the same between the local and central mycology laboratory but the species identification is discrepant, the central laboratory identification will be used. If the local laboratory grows an isolate but the central laboratory is not able to grow the isolate, if isolates were lost during transportation or storage, or there are major discrepancies between the local and central laboratory in the identification of species, the central laboratory will request the local laboratory to resend the isolate. If the central laboratory identification is not available for an isolate, the local laboratory identification will be used. For any remaining major discrepancies in species identification between the central and local laboratory, the central laboratory identification will be used as the default identification. This procedure will be followed for identification of fungal pathogens at baseline and any post-baseline time points.

Any *Candida* species isolated from blood cultures or normally sterile sites will be considered pathogens in this study. Fungal isolates other than *Candida* and bacterial isolates from blood cultures will not be considered pathogens for this study.

CONFIDENTIAL Page 34 of 56

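### Table 1-3 judges only sources that were Candida-positive at baseline, so a new uncleared positive blood or sterile-site culture on study drug can be scored as mycological, and sometimes overall, success

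*SAP*

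**What the plan says.** Mycological response is derived by program from the eCRF and central mycology data under Table 1-3 (SAP section 1.2.6.1). Its culture rules are these:

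- Success, blood: it opens "If positive blood culture at baseline: The last blood culture drawn on or prior to the day of assessment and another blood culture". The pair must be separated by 12 hours or more, and neither may grow Candida.
- Success, sterile site: "If positive culture from a normally sterile site at baseline: Documented mycological eradication: culture on day of assessment from all normally sterile sites", the sites being those infected at baseline. Presumed eradication is the alternative.
- Failure, blood: it opens "If positive blood culture at baseline: The last blood culture drawn on or prior to the day of assessment".
- Failure, sterile site: it opens "If positive culture from a normally sterile site at baseline: Documented mycological persistence: culture on day of assessment from all", with presumed persistence as the alternative.

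Only three matters are judged regardless of baseline source: change of antifungal therapy, death and loss to follow-up. A Note adds that "Subjects with positive cultures from both blood and a normally sterile site will need to meet success criteria for both blood and normally sterile site". Table 1-2 then combines mycological response with systemic signs to give overall response. Success there requires that signs present at baseline have resolved. Failure covers recurrence or non-resolution of attributable signs.

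Section 4 states that any Candida "species isolated from blood cultures or normally sterile sites will be considered pathogens in this study", and applies its identification procedure to isolates after baseline as well.

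**The concern.** A Candida isolate that first appears on study drug, from a source that was clean at baseline, is a mycological event that the response variable ought to register. Under Table 1-3 no culture rule looks at it. Because the derivation is programmatic, no judgment step is specified that would catch it.

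The affected outcomes are mycological and overall response at Day 5, Day 14, Day 28 and Follow-up. Overall response at Day 14 is the primary efficacy outcome and one of the five interim tables listed in section 3.12. The Success wording of Table 1-6 (exploratory mycological response) carries the same baseline conditions. Footnote gg to Table 1-1 has a similar gap: its IC rule, for subjects with or without candidemia, asks only about the sterile site.

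The table is also uneven. In Table 1-4, Example 3 fails a subject with baseline candidemia whose two latest cultures are negative but only 8 hours apart, because a culture 14 hours before the last one was positive. A subject with only IC at baseline whose blood is positive at the assessment itself meets no culture-based failure rule for blood.

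**Working it through.** **Step 1. Is blood covered by the sterile-site rule?** No. Footnote c to Table 1-1 defines IC by a positive culture "from a normally sterile site other than blood", and Table 1-3 treats the two sources separately.

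**Step 2. What is baseline?** Section 3.4 determines baseline Candida from blood and sterile-site samples taken in the 96 hours before randomization. A source that first turns positive later does not trigger a rule conditional on baseline.

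**Step 3. Apply Table 1-3 literally.** In every row the subject is alive and in follow-up.

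| Baseline | At assessment | Therapy | Table 1-3 result |
|---|---|---|---|
| IC only | Baseline site negative, blood positive | Unchanged | Success |
| Candidemia only | Two qualifying negative blood cultures, new sterile site positive | Unchanged | Success |
| Both | Site negative, blood positive | Unchanged | Failure |
| IC only | Baseline site negative, blood positive | Changed | Not Success |

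The first and third rows have the same cultures at assessment. Only the baseline blood result separates Success from Failure. With baseline signs resolved and no attributable signs recurring, Table 1-2 makes the first two rows an overall Success.

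**Step 4. Does other text close the gap?**

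- The Note ("Subjects with positive cultures from both blood and a normally sterile site will need to meet success criteria for both blood") sends the reader back to criteria that each begin with a baseline condition.
- Section 4 settles what an isolate is. It does not link the isolate to response.
- Table 1-5 rules out cure when new attributable signs or symptoms appear, but the investigator's assessment does not feed the primary endpoint. Table 1-2 has no matching provision for new signs.

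**Step 5. Reproduce the plan's figures, then size one subject.** Section 3.1 assumes 73% success. Clopper-Pearson limits with x = 0.73n reproduce its intervals:

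- n = 30, x = 21.9: 53.8% to 87.5%
- n = 60, x = 43.8: 60.0% to 83.7%
- n = 110, x = 80.3: 63.7% to 81.0%

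These planning figures are unaffected. One reclassified subject moves the rate by 1/n:

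- n = 30: 22/30 = 73.3% (54.1% to 87.7%) becomes 21/30 = 70.0% (50.6% to 85.3%), or 3.3 points.
- n = 60: 44/60 = 73.3% (60.3% to 83.9%) becomes 43/60 = 71.7% (58.6% to 82.5%), or 1.7 points.

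If, purely as an assumption, there were 1 to 3 such subjects among 30, the rate would fall from 73.3% to between 70.0% and 63.3% (19/30). Judging more sources only adds conditions for Success, so the present rule can err only upward.

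**The case against.** The strongest reply is that several guards stand between a new isolate and a false overall success. Any change of therapy for candidemia or IC bars Success. Death is a failure. The Failure rows of Table 1-2 mention recurrence of attributable signs without limiting it to signs present at baseline, so a returning fever attributed to new candidemia is an overall failure even with no switch of drug. This stands. It narrows the path to overall success, but signs play a smaller part in the mycological endpoint and none in its blood rule.

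It can also be said that the Note does not repeat the words about baseline, so a subject with only IC at baseline and new positive blood might be held to the blood criterion. That reading is possible, but the criterion's own opening condition contradicts it, and a programmer would have to choose.

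A reader might infer that any on-treatment positive at a new source should have been a failure. The table's own standard does not support that. New positive blood followed by two qualifying negatives would be a success under the baseline-candidemia rule too. A sterile site whose most recent culture is positive can still be presumed eradicated if the clinical outcome is successful. The gap therefore concerns positives not cleared at the assessment. It is plainest for blood; for a sterile site it is clearest when the culture taken on the day of assessment is positive.

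A reader might also see Section 4 as a direct contradiction. It is not one, since it governs identification of isolates. Lastly, section 3.1 describes the study as exploratory and not powered for inference, and the rule applies to all arms alike. Both points limit the consequences.

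**Conclusion.** The point holds. As written, the rule can return mycological Success, and overall Success when baseline signs have resolved, for a subject with an uncleared new positive source at the assessment. It rests on these conditions: the baseline source is cleared or presumed cleared, therapy is unchanged, the subject is alive and in follow-up, and no attributable signs recur.

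Each such subject adds 3.3 points at n = 30 or 1.7 points at n = 60, always upward. How many there would be cannot be derived from the SAP, and any percentage would be an assumption. One subject is small beside a 95% interval of 53.8% to 87.5%. It would go too far to conclude that the primary endpoint is invalid or that the success rates are materially inflated. Severity is moderate: the definition gives a wrong result in a specific situation and should be repaired, but the numerical effect is probably small.

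**What to change.** In Table 1-3, replace the baseline-only triggers so that the existing criteria apply to any source, blood or normally sterile site, that is Candida-positive at baseline or at any time after study drug is started, up to the day of assessment. Then:

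- New positive blood must meet the clearance rule already in the table: in Table 1-3, two negatives at least 12 hours apart with no positive between them; in Table 1-6, a negative last culture.
- A new sterile site must meet the same documented or presumed eradication standard as a baseline site.
- A subject who does not meet the standard is a Failure.

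Make the same change in the Success wording of Table 1-6 and in footnote gg to Table 1-1. The Failure row of Table 1-6 cannot be read in the copy at hand; change it too if it carries the same conditions.

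State also whether an isolate from soon after randomization counts as baseline infection. The mITT2 and mITT3 definitions accept cultures up to 72 hours after randomization as documenting infection, so an early specimen may reveal disease already present.

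The cost is SAP wording, a few lines of programming and possibly a slightly lower success rate. No new data are needed: footnotes ee and ff already send fungal isolates from blood and sterile sites to the Central Laboratory through the last visit.
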